#### Culture Conversion

Culture conversion is defined as MAC culture negative at 2 consecutive visits during the treatment period. The conversion status will be reversed by a positive culture after conversion (recurrence). As such, a subject may achieve culture conversion multiple times during the study. The date of conversion is defined by the date of the first of 2 consecutive negative cultures.

The secondary endpoint culture conversion by Month 6 is defined as MAC culture negative at Month 5 and Month 6 with the adjustment for non-productive sputum (described below) and additional rules described in [Section 9.3.1.2.1](#).

#### Non-productive sputum assessments

If a subject is unable to produce sputum spontaneously, sputum may be induced. If after induction, a subject is still unable to produce sputum despite reasonable efforts, this will be recorded as non-productive at that timepoint.

A non-productive assessment will be considered culture positive if the assessment occurs prior to culture conversion or post recurrence. A non-productive assessment will be considered culture negative if the assessment occurs post culture conversion.

### **9.3.1.2. Analysis**

The endpoint of interest is the proportion of subjects achieving culture conversion by Month 6 as this is the last month of exposure to study medication in this study. The reporting will be presented based on the ITT analysis set and will be provided by randomized treatment group.

The analysis model is the Standardized Logistic Regression (SLR), the model includes response variable, ie conversion status by Month 6 and the following independent variable (stratum at randomization):

- history of MAC lung infection, (initial or subsequent)

The summaries will include:

1. Estimation of group proportions of subjects achieving conversion by Month 6 and difference of these proportions between the treatment groups together with corresponding 95% CIs will utilize the above described SLR model.

The estimation obtained from SLR will be based on the standardized procedure described in [Steingrimsson et al\[13\]](#), the SAS macro %Margin, version 2.0 (or later), provided SAS Institute ([see SAS note <https://support.sas.com/kb/37/228.html>](#)) will be used for implementation.

2. Descriptive statistics, ie, number/frequency of subjects with available assessments and conversion status (ie, rules 1 through 4) will be applied as described in [Section 9.3.1.2.1](#).

### 9.3.1.2.1. Data Handling

For the purpose of the analysis the influence of ICEs ([Section 7.5](#)) and the presence of the missing data on the estimation of culture conversion proportion by Month 6 will be taken into consideration.

Culture conversion by Month 6 will be handled by following rules:

1. Data will be adjusted for non-productive visits
2. A subject who dies after randomization will be considered non-converter by Month 6
3. Retrieved sputum assessments will be used in the analysis, ie, collected after early termination of ALIS/ELC (see [Section 7.4](#) for definition)
4. Subjects with a missing assessment at Month 5 or 6 but not both, will be considered converters by Month 6 if they meet all of the following criteria:
  - achieved culture conversion (2 consecutive monthly negative sputum cultures) at or before Month 5,
  - have negative cultures after conversion with at most 1 missing sputum assessment at or before Month 4,
  - have negative culture at Month 7,
  - do not have recurrence after conversion.

Justification for the rule: The protocol defines culture conversion as no MAC growth on agar media and broth media in all sputum cultures at 2 consecutive visits. Month 6 conversion requires both Months 5 and 6 cultures to be negative for MAC (after non-productivity adjustment); if one of them is missing, culture conversion status cannot be determined. However, in the presence of other post-randomization data, in the instances described above this status may be assigned deterministically, consistent with common clinical practices.

5. Data for subjects who complete 6 months of the randomized treatment however conversion status by Month 6 is not available will be imputed based on the observed status distribution from the subjects who completed 6 months of randomized treatment (ALIS/ELC, AZI, and ETH), have Month 6 conversion

status determined, and were randomized to the same treatment group. This approach is consistent with MAR approach imputation.

6. When retrieved assessments are unavailable or #4 does not provide conversion status by Month 6, the missing Month 6 conversion status will be imputed as follows:
  - For subjects experiencing ICE (other than death), their missing Month 6 conversion status will be imputed based on the retrieved Month 6 conversion distribution from the subjects experiencing ICE (retrievers). MNAR imputation of the data for those subjects experiencing ICE is applied.

Justification for the rule: In most cases, physicians caring for patients discontinuing ALIS/ELC due to an ICE will elect to continue AZI and ETH alone or provide an alternative regimen in order to complete an adequate period of treatment for MAC lung infection. In case of an AE leading to ICE, treatment options for MAC lung disease known to be efficacious other than (at a minimum) the combination of a macrolide plus ethambutol already provided in the study are limited. Furthermore, for ICE patients requiring “rescue therapy” as defined in protocol Section 5.2.2 (ie, a change from randomized treatment due to progression of MAC lung infection), these patients are failing initial course of therapy and should be considered refractory; recommended treatment in that case would be the addition of ALIS – which may or may not have been the cause of the ICE. Therefore, subjects experiencing an ICE are expected to have a microbiologically worse outcome due to limited treatment options following the ICE, and imputation of PROs to the retriever distribution is more representative of their clinical outcome.

- For subjects not experiencing ICE, their missing Month 6 conversion status will be imputed based on the observed status distribution from the subjects who completed 6 months of randomized treatment, have Month 6 conversion status determined, and were randomized to the same treatment group. This approach is consistent with MAR approach imputation.

The ELC treatment group (including retriever) will be used instead if the ICE retriever subgroup is too small to allow imputations as described above. The decision as to which group will be used in the imputation will be determined prior to unblinding at the blinded data review meeting.

Imputation details are included in the [Appendix I](#).

### 9.3.2. QOL-B Patient-reported Respiratory Symptoms at Month 7

#### 9.3.2.1. Variable Description

The QOL-B is a self-administered, reported outcome questionnaire used to assess symptoms, functioning, and health related quality of life in adults with non-CF bronchiectasis (Quittner, 2015). It measures outcomes over a recall period of 1 week. The questionnaire contains 37 items on 8 scales (physical, role, vitality, emotional, social, treatment burden, health perception, and respiratory). There is no overall total score combining all domains of QOL-B.

[Appendix A](#) shows the questionnaire and how the data are captured in the eCRF.

#### Item coding

Each of the 37 items is scored from 1 to 4 with higher scores representing fewer symptoms or better functioning and quality of life.

Before calculating the scale scores, the following preparations are necessary:

- If item 32 = 00 (Green with traces of blood) then item 32 = 1
- If item 32 = 0 (Don't know) then item 32 is set to missing
- If item 19 = 5 (Doesn't apply) then item 19 is set to missing

#### Scale scores

Each of the 8 domain scores is standardized on a 0 to 100-point scale with higher scores representing fewer symptoms or better functioning and quality of life. Positive change from baseline indicates improvement (post therapy score – baseline score > 0).

Scale scores are derived from a subset of items and calculated by

$$scale\ score = \frac{mean\ of\ responses - 1}{3} * 100.$$

If the responses are missing for more than half of the items in a scale, the score for that scale should not be calculated.

Contributing items:

- Physical Functioning Domain (5 items): 1, 2, 3, 4, 16
- Role Functioning Domain (5 items): 17, 20, 25, 27, 28
- Vitality Domain (3 items): 6, 8, 9
- Emotional Functioning Domain (4 items): 7, 10, 11, 23
- Social Functioning Domain (4 items): 18, 19, 22, 26
- Treatment Burden Domain (3 items): 12, 13, 14
- Health Perceptions Domain (4 items): 5, 15, 21, 24
- Respiratory Symptoms Domain (9 items): 29 to 37

The secondary endpoint of interest is the change from baseline to Month 7 in the respiratory symptom domain score. Other domains are exploratory.

#### **9.3.2.2. Analysis**

The analysis of change from baseline to Month 7 in respiratory symptom score (as assessed by QOL-B) will be summarized based on subjects in the ITT analysis set by treatment group.

The analysis model is the ANCOVA, the model includes response variable, ie, change from baseline to Month 7 and the following independent variables:

- history of MAC lung infection, (initial or subsequent)

- baseline QOL-B Respiratory domain score

The regression coefficient for treatment group in the ANCOVA is equal to the estimated population-level average treatment effect of  $\mu_{\text{ALIS}} - \mu_{\text{ELC}}$ ; this estimate will be used in Wald tests deriving p-value for the difference between the treatment groups. The p-value is nominal as the study is not a hypothesis testing and further is not powered for this comparison.

The summaries will include:

1. LS-mean of change from baseline to Month 7, differences of LS-mean changes from baseline (ALIS + background regimen minus ELC + background regimen) estimates and corresponding 95% CIs derived from ANCOVA model.
2. Descriptive statistics by timepoint with corresponding change from baseline.

### 9.3.2.2.1. Data Handling

For the purpose of the analysis the influence of ICEs and the presence of the missing data on the estimation of change from baseline to Month 7 PRO means will be taken into consideration. The ICEs are defined as post-randomization events leading to early ALIS/ELC therapy termination due to death, ALIS/ELC-related TEAE, use of rescue medication, or lack of efficacy.

Change from baseline to Month 7 will incorporate the following considerations:

1. A subject who dies after randomization will be assigned the worst observed change score in the entire sample as the change from baseline to Month 7
2. Retrieved Month 7 assessments will be used in the analysis, ie, collected after early termination of ALIS/ELC (see [Section 7.4](#) for definition)
3. Data for subjects who complete 6 months of the randomized treatment however their Month 7 PRO is not available will be imputed based on the observed status distribution from the subjects who completed 6 months of randomized treatment (ALIS/ELC, AZI and ETH), have Month 7 available, and were randomized to the same treatment group. This approach is consistent with MAR approach.
4. When retrieved assessments are unavailable the missing change from baseline to Month 7 will be imputed as follows:
  - For subjects experiencing ICEs other than death, their missing Month 7 PRO will be imputed based on the retrieved assessment distribution from those retrievers who experienced ICE and are exposed to an altered treatment regimen after their ICEs. MNAR imputation of the data for those subjects experiencing ICE is applied.

Justification for usage of retrievers' data is included in [Section 9.3.1.2.1](#).

- For subjects not experiencing ICE, their missing Month 7 PRO data will be imputed based on the observed data distribution from the subjects who completed 6 months of randomized therapy (ALIS/ELC, AZI and ETH), have Month 7 PRO data assessment available, and are randomized to the same treatment group. This approach is consistent with Missing-at-Random (MAR) approach.

Imputation details are included in [Appendix I](#).

The ELC treatment group will be used instead if the ICE retriever subgroup is too small to allow imputations as described above. The decision as to which group will be used in the imputation will be determined prior to unblinding at the data review meeting.

The results of the analyses for each imputation will be combined using Rubin's rule.

### 9.3.2.3. Sensitivity Analysis

As sensitivity analysis, a different rule for obtaining the combined p-value from the analysis of the multiple imputation will be applied.

Wald Chi-Square statistics will be calculated and will be combined using Rubin's rule result in a single combined p-value.

## 9.3.3. Patient-reported Fatigue Symptoms at Month 7 - PROMIS Fatigue

### 9.3.3.1. Variable Description

The PROMIS F-SF 7a is a self-administered questionnaire assessing a range of self-reported symptoms over the past 7 days, from mild subjective feelings of tiredness to an overwhelming, debilitating, and sustained sense of exhaustion that likely decreases one's ability to execute daily activities and function normally in family or social roles ([Ameringer, 2016\[1\]](#)). Fatigue is divided into the experience of fatigue (frequency, duration, and intensity) and the impact of fatigue on physical, mental, and social activities over 7 items.

Response options are on a 5-point Likert scale, ranging from 1=never to 5=always.

#### Item coding

Item FATIMP40 must be recoded from (1=never, ...,5=always) to (1=always, ..., 5=never) as shown in [Appendix B](#) before any further scoring.

#### Raw score

The raw score is the sum of responses to all 7 questions, ranging from 7 to 35. Lower values represent a better state of health.

#### T-score

The T-score rescales the raw score into a standardized score with a mean of 50 and a standard deviation (SD) of 10.

**Table 3: Scoring table PROMIS F-SF 7a**

Raw Score	T-score	Raw Score	T-score	Raw Score	T-score
7	29.4	17	52.2	27	66.3
8	33.4	18	53.7	28	67.8
9	36.9	19	55.1	29	69.4
10	39.6	20	56.4	30	71.1
11	41.9	21	57.8	31	72.9
12	43.9	22	59.2	32	74.8
13	45.8	23	60.6	33	77.1
14	47.6	24	62.0	34	79.8

15	49.2
16	50.8

25	63.4
26	64.8

35	83.2
----	------

### 9.3.3.2. Analysis

Change from baseline to Month 7 in fatigue symptom raw score (as assessed by PROMIS F-SF 7a) will be analyzed similarly to QOL-B respiratory symptoms domain, see [Section 9.3.2.2](#) for details.

Depending on the outcome of the Validation Report it is possible that the scoring algorithm will change, in such case an analysis based on the modified scoring algorithm will be provided.

### 9.3.4. Time to Culture Conversion

#### 9.3.4.1. Variable Description

Time to culture conversion is the number of months from the date of first dose of study drugs to the date of the first culture conversion. For the purpose of this analysis, naming convention will be adopted according to the first of the two cultures being negative. For example, culture conversion at Month 3 will require Month 3 and Month 4 cultures to be negative. This definition was adopted since the first culture being negative is an indication of clinical improvement.

Time to culture conversion (months) =

$$(\text{date of culture conversion} - \text{date of first dose of drug intake} + 1) / 28^*$$

\* rounded to the nearest month

Time to conversion will be set to number of months between first study drug(s) intake and date of the first negative culture (in the sequence of the two negative). A subject who died will be considered censored at the last visit with available culture assessment.

Subjects without conversion are considered censored. Time of censoring is set to the last visit with available culture assessment up to and including Month 6.

It should be noted that the definition of culture conversion at Month 1 through Month 6 differ from the definition of culture conversion by Month 6 ([Section 9.3.1.1](#)). Time to conversion evaluates the specific timepoint at each culture conversion is achieved. Culture conversion by Month 6 evaluates the cumulative culture status up to and including Month 6.

#### Cumulative conversion summary for Culture Conversion by Month 6

In addition, an analysis will be performed to include Month 1 through Month 5 cumulative conversion summary. Denominator for this cumulative analysis is number of subjects who converted by Month 6 (rules 1 through 4 will be applied as described in [Section 9.3.1.2.1](#)).

#### Cumulative conversion summary for Culture Conversion by Month 7

An analysis will be performed to include Month 1 through Month 6 cumulative conversion summary. Denominator for this cumulative analysis is number of subjects who converted by Month 7 (rules will be applied as described in [Section 11.3](#)).

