#### 3.2. Secondary Objectives and Endpoints

To evaluate the effect of each treatment arm (ALIS + background regimen and ELC + background regimen) on the following:

Objective	Endpoint
Culture conversion by Month 6	Proportion of subjects achieving culture conversion by Month 6 (negative cultures for MAC at Month 5 and Month 6)
Patient-reported respiratory symptoms at Month 7	Change from Baseline to Month 7 in respiratory symptom score
Patient-reported fatigue symptoms at Month 7	Change from Baseline to Month 7 in fatigue symptom score

Objective	Endpoint
Time to culture conversion	Time to culture conversion (first of 2 consecutive negative cultures) of Baseline to EOT assessments
Time to first negative culture	Time to first negative culture of Baseline to EOT assessments
MAC isolates with amikacin MIC $\geq 128$ $\mu\text{g}/\text{mL}$	Proportion of subjects who develop a MAC isolate with amikacin MIC $\geq 128$ $\mu\text{g}/\text{mL}$ at more than 1 visit at any timepoint during the study
Recurrence of MAC (relapse)	Proportion of subjects who achieved culture conversion and subsequently have at least 1 MAC positive culture in agar media or positive cultures in broth media in at least 2 consecutive visits that is the same species and genome as cultured at Screening/Baseline.
Recurrence of MAC (new infection)	Proportion of subjects who achieved culture conversion and subsequently have at least 1 MAC positive culture in agar media or positive cultures in broth media in at least 2 consecutive visits that is different than cultured at Screening/Baseline (different species or same species but different genome).
Safety and tolerability of ALIS + background regimen	Incidence and severity of AEs and TEAEs and other safety variables (eg, vital signs, physical examination, clinical laboratory values) from Baseline through the EOS

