#### 9.3.4.2. Analysis

Unless otherwise stated analysis of time to culture conversion will be summarized as follows:

1. Basic statistics of time to conversion
2. Number of observations, number of censored observations, number at risk (by visit)
3. Hazard ratio (ALIS + background regimen: ELC + background regimen) and corresponding 95% CIs,
4. Kaplan-Meier plot will be provided
5. A Cox regression model will be applied to calculate the hazard ratio. The model includes effects for treatment and stratification variable (history of MAC lung infection, initial or subsequent).

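### Time to culture conversion: events are dated at the first of two negative cultures but censoring is at the last culture, so the risk set includes subjects who could not have a confirmed event (a small bias, cheap to remove)

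*SAP*

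**What the plan says.** SAP 9.3.1.1 sets the event date: "The date of conversion is defined by the date of the first of 2 consecutive negative cultures". SAP 9.3.4.1 repeats this with an example: "For example, culture conversion at Month 3 will require Month 3 and Month 4 cultures to be negative". An event at one visit thus depends on the culture at the next.

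Censoring does not follow the same logic. For subjects without conversion, "Time of censoring is set to the last visit with available culture assessment up to and including Month 6". For deaths, "A subject who died will be considered censored at the last visit with available culture assessment". SAP 9.3.4.2 then takes these times into the number at risk by visit, the Kaplan-Meier plot and a Cox hazard ratio adjusted for history of MAC lung infection. Its first listed item is "Basic statistics of time to conversion".

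The SAP is not consistent on the last visit at which an event can be dated. SAP 9.3.4.1 says "It should be noted that the definition of culture conversion at Month 1 through Month 6 differ" from the by-Month-6 definition, which implies that Month 7 can confirm Month 6. SAP 9.3.1.1 says "Culture conversion is defined as MAC culture negative at 2 consecutive visits during the treatment period", and SAP 3.2 lists the endpoint as "Time to culture conversion (first of 2 consecutive negative cultures) of Baseline to EOT assessments". Those two point to Month 6 as the last usable culture and Month 5 as the last event visit.

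**The concern.** Take a subject whose last culture is at Month 3. Conversion at Month 3 would need a Month 4 culture, which does not exist. Whatever the Month 3 culture showed, this subject cannot be recorded as an event at Month 3, yet the rule keeps the subject in the Month 3 risk set. The status is unknown but is counted as no conversion.

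Every subject lost in this way adds to the denominator at one visit without any chance of adding to the numerator, so the estimated hazard at that visit is too low. If the arms lose subjects at different rates, the hazards are lowered by different amounts and the hazard ratio moves. Nothing else in the SAP corrects this: the data-handling rules in 9.3.1.2.1 and the multiple imputation in Appendix I deal with conversion status by Month 6 or Month 7, not with this time variable. Time to first negative culture (9.3.5.1) has a similar censoring rule but is sound, because a single culture decides the event.

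**Working it through.** The documents give no event count, power or hazard ratio for time to conversion, so there is no stated figure to reproduce.

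**Inputs from the SAP.** Event and censoring rules: 9.3.1.1 and 9.3.4.1. Conversion of 50%, 60% or 70%, missing data of 0%, 5% or 20%, and 50 subjects per arm: 4.3.1. Those planning values belong to the PRO power simulation and are borrowed here for scale.

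**Assumptions not in the documents.** Constant monthly hazard; missing data read as permanent loss, independent of conversion; loss spread evenly over Months 1 to 5 unless stated; the split of loss and of conversion between arms.

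**Formula.** Let L be the visit of the last culture, h the true hazard per visit, and q_t = P(L = t given L ≥ t). Under the SAP rule, subjects at risk at t have L ≥ t, but an event at t is seen only if L ≥ t+1. The estimated hazard is therefore h × (1 − q_t). If subjects are instead censored at L − 1, those at risk at t all have L ≥ t+1 and the estimated hazard is h.

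**Conversion, Month 7 may confirm Month 6.** True conversion is 60% over six visits, so h = 1 − 0.4^(1/6) = 0.1416. Loss of 20% means 4% of the cohort has its last culture at each of Months 1 to 5:

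- q_t = 0.04/1, 0.04/0.96, 0.04/0.92, 0.04/0.88, 0.04/0.84, 0
- 1 − q_t = 0.9600, 0.9583, 0.9565, 0.9545, 0.9524, 1
- h(1 − q_t) = 0.1360, 0.1357, 0.1355, 0.1352, 0.1349, 0.1416
- estimated conversion = 1 − product of (1 − h(1 − q_t)) = 1 − 0.4146 = 58.5%

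**Conversion, Month 6 is the last usable culture.** Over five visits h = 1 − 0.4^(1/5) = 0.1674. The same steps give 58.2%.

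| Loss | Estimate of a true 60%, last event Month 6 | Last event Month 5 |
|---|---|---|
| none | 60.0% | 60.0% |
| 5% | 59.7% | 59.6% |
| 20% | 58.5% | 58.2% |

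Over true conversion of 50% to 70% and both readings, the shortfall is 0.3 to 0.4 points at 5% loss and 1.3 to 1.8 points at 20%. Censoring at L − 1 returns the true value in each case.

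**Hazard ratio.** With 20% loss on ALIS and 5% on ELC, the monthly ratio of the two multipliers runs from 0.9600/0.9900 = 0.970 at Month 1 to 0.9524/0.9896 = 0.962 at Month 5, and is 1 at Month 6. The expected Cox estimate (Efron ties) averages these:

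| Loss, ALIS vs ELC (assumed) | True 1.00, last event Month 6 | True 1.00, last event Month 5 | 70% vs 50%, last event Month 6 (true 1.735) |
|---|---|---|---|
| 20% vs 20%, even | 1.000 | 1.000 | 1.732 |
| 20% vs 5%, even | 0.968 | 0.964 | 1.678 |
| 20% in Months 1–2 vs 5% even | 0.957 | 0.949 | 1.659 |
| 20% at Month 1 vs none | 0.945 | 0.934 | 1.639 |
| 5% vs 20%, even | 1.033 | 1.037 | 1.791 |

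Censoring at L − 1 restores 1.00 or 1.735 in every row.

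**Size against sampling error.** A culture-level simulation at 50 per arm (20% vs 5% loss) gave a standard deviation of the log hazard ratio of 0.28. The bias on the log scale runs from ln 0.968 = −0.033 to ln 0.934 = −0.068. Dividing, 0.033/0.28 = 0.12 and 0.068/0.28 = 0.24.

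**The case against.** The strongest reply is that little depends on this. SAP 7.2 makes every summary descriptive and every p-value nominal. The primary objective is PRO validation, and conversion by Month 6 has its own missing-data rules that do not use this censoring time. Loss here means no further culture, not stopping drug: subjects who stop a drug continue scheduled visits (Protocol 4.2.1) with all efficacy assessments (SAP 4.1), and those who leave early are asked to attend EOT and EOS visits (Protocol 4.2.3), where sputum is scheduled. Non-productive visits before conversion count as positive and fully contaminated visits as negative, so neither is missing. With complete cultures there is no understatement. All of this stands. It limits the size but does not make the rule right.

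A reader might infer that an ALIS effect will be understated. The documents do not support that. Protocol 9.9.6 reports that in the refractory-disease study most ALIS subjects had their first adverse event within 60 days, which makes unequal early loss conceivable, but no document gives loss by arm, and the last row of the table shows the bias reversing if ELC loses more.

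A reader might also infer that the basic statistics in 9.3.4.2 will hide a real difference between arms. The SAP does not say how they treat censored times, and the planned Kaplan-Meier plot lets medians be read off where they are reached. Tabulating those medians is a reporting preference.

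**Conclusion.** The censoring rule does not match the event definition, and no other SAP section repairs it for this endpoint. The mechanism follows from the SAP's wording alone; its size rests on the assumptions listed above. At the plan's own missing-data values the understatement of conversion is below two percentage points. The hazard ratio is materially unaffected unless loss differs between arms, and even then the bias is well inside sampling error at this sample size. The documents do not support calling the hazard ratio seriously distorted, or extending the point to conversion by Month 6 or to the primary objective. The change is still worth making: this is a listed secondary endpoint, the estimate should match its definition, and the correction costs almost nothing. The unsettled role of the Month 7 culture should be resolved at the same time, because it fixes the last event visit and hence the censoring limit.

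**What to change.** In SAP 9.3.4.1, replace the two censoring sentences with a rule along these lines: subjects without conversion, including those who die, are censored at the last visit for which the culture at that visit and the culture at the next scheduled visit are both available, whatever the last culture shows, and no later than the last visit at which conversion can be dated; if there is no such post-baseline visit, they are censored at first dose. Moving only those subjects whose last culture is an unconfirmed negative would leave the risk set biased.

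State in 9.3.1.1 and 9.3.4.1 whether the Month 7 culture may confirm a Month 6 conversion. If yes, the latest event and censoring visit is Month 6; if no, it is Month 5.

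The rule should not be shortened to the visit before the last available culture. With cultures at Months 1, 2, 3 and 5 and none at Month 4, the rule above censors at Month 2, and the shorter wording does not. Nor does the rule fully cure an isolated gap: with cultures at Months 1, 2, 3, 5 and 6, the subject stays at risk at Months 3 and 4 with no confirmable event. The SAP should acknowledge this.

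Optionally, add to 9.3.4.2 the Kaplan-Meier median with its 95% CI and the proportion converted by visit, alongside the basic statistics.

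Cost: a few sentences and a small programming change. A few subjects leave the risk set one visit earlier, so intervals are very slightly wider.
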